8.2 EXCLUSION CRITERIA

- 1. Use of any other standard anti-neoplastic drug or growth factor (e.g., anagrelide, G-CSF, lenalidomide, thalidomide clofarabine) except hydroxyurea or experimental drugs, with the exception of ruxolitinib or enasidenib, less than 14 days or 5-half-lives, whichever is longer, prior to starting study therapy and/or lack of recovery from all toxicity (except for alopecia) from previous therapy to Grade 1 or better.
 - a. Patients will be permitted to receive hydroxyurea while on study for up to a total of 3 cycles of combined therapy.
- 2. Known prior clinically relevant hypersensitivity reaction to ruxolitinib or enasidenib.
- 3. Prior therapy with enasidenib in combination with ruxolitinib.
- 4. Concurrent use of strong inducers of CYP3A4 (Rifampin, St. John's Wort, Carbamazepine, Phenytoin) and/or the following strong inhibitors of CYP3A4 (protease inhibitor containing HIV anti-retrovirals, cobicistat, clarithromycin, itraconazole, ketoconazole, nefazodone, and telithromycin) are prohibited. Also prohibited are CYP2C9 substrate medications that have a narrow therapeutic range: phenytoin and warfarin.
- 5. Any serious medical condition, laboratory abnormality, or psychiatric illness that would prevent the subject from signing the informed consent form, which places the subject at unacceptable risk if he/she were to participate in the study or which confounds the ability to interpret data from the study.
- 6. Lactating females.
- 7. Active uncontrolled infections.
- 8. Patients with active malignancy of other type than required for this study are not eligible with the exception of currently treated basal cell, squamous cell carcinoma of the skin, or carcinoma "in situ" of the cervix or breast. Patients with malignancies with indolent behavior such as prostate cancer treated with radiation or surgery can be enrolled in the study as long as they have a reasonable expectation to have been cured with the treatment modality received.
- 9. Subject has significant active cardiac disease within 6 months prior to the start of study treatment, including New York Heart Association (NYHA) Class III or IV congestive heart failure (Appendix G) acute coronary syndrome (ACS); and/or stroke; or left ventricular ejection fraction (LVEF) < 40% by echocardiogram (ECHO) or multi-gated acquisition (MUGA) scan obtained within 28 days prior to the start of study treatment.

MPN-RC A Phase II Open-label Study of Combined Ruxolitinib and Enasidenib Sinai in Patients with Accelerated/Blast-phase Myeloproliferative Neoplasm or Chronic-

phase Myelofibrosis with an IDH2 Mutation

(Myeloproliferative Neoplasms Research Consortium [MPN-RC] 119)

10. QTc interval (Fridericia's correction [QTcF]) > 450 ms

All inclusion and exclusion criteria will be reviewed by the Investigator or qualified designee to ensure that the patient qualifies for the trial.

9.0 SUBJECT RECRUITING AND SCREENING

Patients will be recruited from the sites participating in the MPN-RC. It is expected that a maximum of 32 patients will be recruited to this study. The estimated accrual rate is 2-3 patients per month.

9.1 STUDY-WIDE RECRUITMENT METHODS

Potential research subjects will be identified by a member of the patient's treatment or research teams. If the Investigator is a member of the treatment team, s/he will screen their patient's medical records for suitable research study participants and discuss the study and their potential for enrolling in the research study. Potential subjects contacted by their treating physician will be referred to the Investigator/research staff of the study. The extent of the risks, benefits, toxicities/side effects, alternatives/options for treatment, financial costs/burdens, and the voluntary nature of the study will be explained to patients. All patients will be required to sign a written informed consent prior to being registered on this protocol. Every effort will be made to answer questions raised by patients and their families or advocates regarding the protocol and alternative therapies prior to asking a patient to sign the consent form.

Patients of all races, both male and female, will be accepted into the protocol.

10. TREATMENT DOSAGE AND ADMINISTRATION

Patients who are on ruxolitinib will continue their current dose. Patients who are not on ruxolitinib will receive ruxolitinib per Table 1 dosing based on platelet count (modified package insert dosing). Enasidenib will be given at 100 mg daily on enrollment for patients with accelerated and blast phase myelofibrosis regardless of platelet count (this will be deemed Cycle 1). Patients with chronic phase myelofibrosis will receive Enasidenib at starting dose of 50 mg daily for cycle 1. The dose of Enasidenib will be increased to 100 mg for cycle 2 if the platelet count stays above 50,000 at the end of cycle 1 (Table 3a) and no other therapy emergent SAE of grade \geq 2 developed (except grade 2 hyperbilirubinemia that is acceptable for dose escalation).

Ruxolitinib and enasidenib will be given orally in an outpatient setting unless the patient is being seen inpatient for another reason. Ruxolitinib and enasidenib will be given orally in 28-day cycles.

Patients should fast 2 hours before and 1-hour post enasidenib. Ruxolitinib may be administered independent of fasting and may be given with enasidenib. All protocol mandated visits will be performed at one of the participating institutions. Patients will return to the treating institution at a minimum of weekly during Cycles 1 and 2, every 4 weeks for Cycles 3 and beyond. Additional clinic visits will be mandated according to the patient clinical condition and at the discretion of the treating provider. Patients will have an end of study visit for a safety follow-up at 30 days after their last dose of therapy.

The dosages of ruxolitinib and/or enasidenib can be reduced, based on assessment of adverse events, if any occur, as described below in Section 10.1. Missed or vomited doses of ruxolitinib or enasidenib will not be made up.

Twenty-eight days is considered one cycle of therapy. Attempts will be made to provide an adequate treatment period with the combination of at least 6 cycles, unless significant toxicity is observed, to account for delayed time to response observed with biologic agents. Responders will continue therapy indefinitely unless progression of disease occurs, toxicity warranting discontinuation of therapy is

A Phase II Open-label Study of Combined Ruxolitinib and Enasidenib Sinai in Patients with Accelerated/Blast-phase Myeloproliferative Neoplasm or Chronic-

phase Myelofibrosis with an IDH2 Mutation

(Myeloproliferative Neoplasms Research Consortium [MPN-RC] 119)

observed, or at the discretion of the treating physician. Patients will have an end of study visit for a safety follow-up at 30 days after their last dose of therapy.

10.1 DOSE MODIFICATION FOR NON-HEMATOLOGICAL AE'S, CLINICALLY SIGNIFICANT IN THE OPINION OF THE TREATING PHYSICIAN

Based on available pharmacokinetic and drug metabolism data, ruxolitinib is mainly metabolized by CYP3A4 with additional contribution from CYP2C9. Enasidenib inhibits CYP2C9 and induces CYP3A4. Although no adjustment is recommended when ruxolitinib is co-administrated with CYP3A4 inducer, potential drug-drug interactions might occur. This study will be the first time ruxolitinib and enasidenib will be used in combination for this patient population. Therefore, the safety of the combination will be confirmed in the first six patients who accrue. If no more than one patient out of the initial six has a treatment-related Grade 3 or higher adverse event attributable to the study drugs, the combination therapy will be considered safe. If more than one patient out of the initial six has limiting toxicity, the trial will be suspended, and the safety data will be further reviewed.

If drug-related Grade 3 clinically relevant non-hematologic toxicity is attributable to one or both of the drugs (based on known adverse events profile), dose interruption of that particular drug(s) is mandatory. Patients who experience Grade 3 drug related clinically relevant non-hematological toxicity may be given a subsequent course one dose level below the previous course, but the patient must have recovered to Grade ≤ 1 before initiation of the next course. If attributable to ruxolitinib, dosing modifications in Tables 2a and 2b should be utilized. If attributable to enasidenib, dosing modification in Table 3b should be utilized. If a patient has drug-related clinically relevant Grade 4 non-hematologic toxicity, he/she will be taken off study. The dose of therapeutic agents can be decreased, at the discretion of treating physician, for chronic Grade 2 non-hematologic toxicity. Additionally, ruxolitinib dosage may be adjusted if patients develop decline in Creatinine clearance (CrCl) as calculated by the Cockcroft- Gault equation as follows: Reduce ruxolitinib dose by one dose level for patients with moderate (CrCl 30-59 mL/min) or severe renal impairment (CrCl 15-29 mL/min) if the patient is receiving a ruxolitinib dose of 10 mg BID or higher. (Per FDA package insert for ruxolitinib).

Myelosuppression and cytopenias are expected outcomes of MF disease processes and MF treatments and per se will not constitute adverse events except as follows: hematologic toxicity will be considered Grade 4 neutropenia with fever that does not clinically resolve within 14 days in the setting of optimal interventions or Grade 4 thrombocytopenia with clinically-significant bleeding. Dose interruption of the drug to which the adverse event is attributable is required. Patients may be given a subsequent course one dose level below the previous course, but the patient must have recovered to grade \leq baseline at study entry. The dose of therapeutic agents can be decreased, at the discretion of treating physician, for chronic Grade 3 hematologic toxicity.

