10.5 IDH-INHIBITOR DIFFERENTIATION SYNDROME (IDH-DS)

in Patients with Accelerated/Blast-phase Myeloproliferative Neoplasm or Chronicphase Myelofibrosis with an IDH2 Mutation

(Myeloproliferative Neoplasms Research Consortium [MPN-RC] 119)

Subjects treated with enasidenib may develop signs and symptoms of a IDH-Inhibitor Differentiation Syndrome (IDH-DS). This may include any of the following: unexplained fever, skin rash, leukocytosis, thrombocytosis, hypoxia, respiratory distress, interstitial pulmonary infiltrates, pleural and/or pericardial effusion, peripheral edema, weight gain, or clinical deterioration. No single sign or symptom may be considered per se as diagnostic of the syndrome. It is recommended that the prophylactic and therapeutic measures indicated below be undertaken at the earliest manifestations of suspected IDH-Inhibitor Differentiation Syndrome (IDH-DS):

- Enasidenib may be held at the Investigator's discretion, and must be held if severe symptoms persist after 48 hours of systemic steroid administration.
- Prompt initiation of hydroxyurea at a suggested dose of 2 to 3 g PO two or three times daily.
- Prompt administration of corticosteroids at a suggested dose of 10 mg of dexamethasone intravenously (IV) every 12 hours until the disappearance of symptoms and signs, and for a minimum of 3 days.
- Initiation of furosemide per local standard practice, if clinically required.
- Prompt initiation of leukapheresis, if clinically required.

Once the signs and symptoms resolve and the subject's clinical condition improves, enasidenib may be reinitiated. The dose of enasidenib at re-initiation is to be discussed with the Study Chair.

For more information See Appendix D.

MPN-RC

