18.2.1 SIDE EFFECTS

Reported specific adverse drug reactions of enasidenib includes the following:

- Hematologic adverse events include: neutropenia and leukocytosis
- Non-hematologic adverse events include: IDH-DS

TLS, GI disturbances (such as nausea, diarrhea, vomiting, and associated dysgeusia and decreased appetite), and hyperbilirubinemia.

A Phase II Open-label Study of Combined Ruxolitinib and Enasidenib Sinai in Patients with Accelerated/Blast-phase Myeloproliferative Neoplasm or Chronic-

phase Myelofibrosis with an IDH2 Mutation

(Myeloproliferative Neoplasms Research Consortium [MPN-RC] 119)

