- The study drug may be withheld at the investigator's discretion. Due to long half-life of the IDH-inhibitors, treatment interruption may not immediately reverse symptoms of IDH DS. Potential for drug-drug interaction between IDH inhibitor and treatments initiated for management of IDH DS should be considered, when making decisions about study drug treatment interruption. If interrupted, study drug treatment may be reinitiated at the original or reduced dose once the signs and symptoms resolve and the subject's clinical condition improves.

A Phase II Open-label Study of Combined Ruxolitinib and Enasidenib Sinai

in Patients with Accelerated/Blast-phase Myeloproliferative Neoplasm or Chronicphase Myelofibrosis with an IDH2 Mutation

(Myeloproliferative Neoplasms Research Consortium [MPN-RC] 119)

- If renal dysfunction or severe pulmonary symptoms requiring intubation or ventilator support persist for more than 48 hours after initiation of systemic corticosteroids, interrupt enasidenib treatment until signs and symptoms are no longer severe
- In subjects with elevated WBC, prompt initiation of hydroxyurea is suggested, as per standard local practices (e.g., dose of 2 to 3g PO twice or three times daily for WBC >30x10⁹/L)
- In cases of severe leukocytosis, use of leukapheresis may be appropriate
- For substantial fluid accumulation, initiation of furosemide may be appropriate, as per local standard practice
- Pericardial effusion a less common symptom of IDH DS can be life threatening condition requiring urgent intervention
- Subjects with increasing serum creatinine levels should be evaluated for TLS
- Subjects experiencing rapid increase in peripheral blood cells should be monitored for disseminated intravascular coagulopathy and hemorrhages
- Imaging techniques such as standard or high-resolution CT or chest X-ray are useful in establishing a diagnosis of IDH DS. However, chest X-ray is less sensitive in detecting early radiological signs of IDH DS associated changes.

Immediate communication with the Study Co-Chairs is encouraged for guidance regarding treatment.

MPN

Mount The Ti A Phase II Open-label Study of Combined Ruxolitinib and Enasidenib Sinai in Patients with Accelerated/Blast-phase Myeloproliferative Neoplasm or Chronicphase Myelofibrosis with an IDH2 Mutation

(Myeloproliferative Neoplasms Research Consortium [MPN-RC] 119)

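### For Grade 3 or 4 IDH differentiation syndrome, Section 10.1 conflicts with Section 10.5 and Appendix D on hold, restart dose and removal, and no text says which governs

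*Combined protocol and SAP*

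**What the plan says.** **Section 10.1 (general non-hematologic rule).** For drug-related, clinically relevant Grade 3 toxicity, "dose interruption of that particular drug(s) is mandatory". Afterwards the patient "may be given a subsequent course one dose level below the previous course, but the patient must have recovered to Grade ≤ 1" before the next course. For Grade 4: "If a patient has drug-related clinically relevant Grade 4 non-hematologic toxicity, he/she will be taken off study".

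**Section 10.5 (IDH-DS).** "Enasidenib may be held at the Investigator's discretion, and must be held if severe symptoms persist after 48 hours of systemic steroid administration". Enasidenib may be restarted once signs and symptoms have resolved and the patient has improved. On the dose: "The dose of enasidenib at re-initiation is to be discussed with the Study Chair". The section then points to Appendix D for more information.

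**Appendix D (Section 34.4, IDH-DS guidance).** Withholding the drug is at the investigator's discretion. If it was interrupted, "study drug treatment may be reinitiated at the original or reduced dose once the signs and symptoms resolve". For renal dysfunction, or pulmonary symptoms needing intubation or a ventilator, that lasts more than 48 hours on corticosteroids, the instruction is to "interrupt enasidenib treatment until signs and symptoms are no longer severe". The appendix describes itself as guidance to be individualized.

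**Section 18.2.1 (enasidenib side effects).** "Non-hematologic adverse events include: IDH-DS". Section 18.3 also lists IDH-DS under non-hematologic effects.

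**The concern.** The three texts address the same event and set different obligations. An investigator with a Grade 3 or 4 case finds a compulsory rule in one section and discretion in another, with no order of precedence.

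The stake is mainly patient safety. Section 6.3 reports a fatal cardiac tamponade in the earlier enasidenib study, where the pericardial effusion was judged in retrospect a likely sign of IDH-DS. There is also a conduct problem. Sites may handle like cases differently, and a site that follows Section 10.5 to the letter may be recorded as deviating from Section 10.1.

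**Working it through.** The protocol gives no design figure on this point, so the check is a comparison of the texts, followed by a short calculation of how likely IDH-DS is to occur.

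**Step 1. Does Section 10.1 reach IDH-DS?** Section 10 refers dose reductions for adverse events to Section 10.1. That section covers drug-related, clinically relevant non-hematologic toxicity, and Sections 18.2.1 and 18.3 list IDH-DS as non-hematologic. Section 10.1 contains no exemption for it.

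**Step 2. Is there a precedence statement?** None was found in Section 10.1, Section 10.5 or Appendix D, or elsewhere.

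**Step 3. Apply each text to the same case.**

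| Question | Section 10.1 | Section 10.5 | Appendix D |
|---|---|---|---|
| Grade 3, at onset: hold? | Compulsory | Investigator's choice | Investigator's choice |
| Grade 3, restart dose | One level lower | Discuss with Study Chair | Original or reduced |
| Grade 3, condition for restart | Grade 1 or less | Signs and symptoms resolved, patient improved | Resolved, with improvement; the ventilator/renal bullet ends the interruption once no longer severe |
| Grade 4 | Off study | No removal rule; restart foreseen | No removal rule; restart foreseen, even after ventilator support |
| Compulsory hold at 48 hours on steroids | Not used | Any severe symptoms that persist | Only renal dysfunction, or pulmonary symptoms needing intubation or ventilation |

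The first four rows set Section 10.1 against the IDH-DS texts and are the main conflict. The last row is a secondary difference between Section 10.5 and Appendix D. Appendix D's own severe category also includes worsening dyspnea or hypoxia, bilateral infiltrates, and pleural or pericardial effusion. A severe pericardial effusion that persists beyond 48 hours on steroids therefore triggers the compulsory hold in Section 10.5 but not the interruption bullet in Appendix D.

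**Step 4. Can the cases in conflict be counted?** No. Appendix D's severe category is not mapped to CTCAE grades, and no rate is given by grade. Section 16.2 defines Grade 4 as being at risk of death, but only where no CTCAE grading exists, so even a ventilated case is not assigned a grade by the documents.

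**Step 5. Is IDH-DS likely to occur at all?** Inputs: 7.3% reported as serious (24 of 330, Section 6.3); 14% overall (Section 18.3; Appendix D says at least 14%); maximum enrollment 32 (Section 21). Assumption: these rates carry over to this population and combination.

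- Expected cases, n × p: 32 × 0.073 = 2.3; 32 × 0.14 = 4.5.
- Chance of at least one, 1 − (1 − p)^n: 1 − 0.927^32 = 0.91; 1 − 0.86^32 = 0.99.

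These figures count IDH-DS cases of any grade (14%) or serious cases (7.3%), not Grade 3 or 4 cases. Section 16.2.1 itself says that serious and severe are different things.

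**The case against.** **The specific section overrides the general one.** Section 10.5 is a separate section for this event. The QT rules in Section 10.1.1 show that the protocol uses event-specific rules: they set their own recovery test at Grade 3 and, at Grade 4, discontinue enasidenib permanently rather than taking the patient off study. Section 10.1 is also confined to events the treating physician considers clinically significant. This reading is plausible, but the protocol never states it. The QT rules also follow the direction of Section 10.1 (interrupt and reduce at Grade 3, no restart of enasidenib at Grade 4), so they do not show that event-specific text displaces it.

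**The stricter rule satisfies every text.** An investigator who holds at onset and restarts lower breaches none of the three on hold or restart dose. That is true, but nothing tells the investigator to do so, and it would empty the discretion in Section 10.5 for Grade 3 cases.

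**The side-effect lists are descriptive.** Leukocytosis is listed as hematologic in Section 18.2.1 and as non-hematologic in Section 18.3, so these lists are a weak basis for dose rules. This stands as a caution. IDH-DS, however, is non-hematologic in both.

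**Three mutually incompatible rules.** A reader might infer these on every point, and the documents do not support it. Only Section 10.1 has a removal rule. Sections 10.5 and Appendix D can be read together on restart dose, since a discussion with the Study Chair may end in the original dose. Appendix D is guidance, and its permissive hold does not cancel the compulsory hold in Section 10.5.

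**Safeguards exist.** Appendix D calls for hospitalization of severe or rapidly progressing cases and encourages immediate contact with the Study Co-Chairs. Section 27 stops treatment for events that may cause severe or permanent harm. These reduce the risk but do not settle which rule applies.

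**Conclusion.** The conflict is real and confined to IDH-DS graded 3 or 4: Section 10.1 against Section 10.5 and Appendix D on the initial hold, the restart dose and the handling of Grade 4. The mismatch in the 48-hour trigger is secondary. The conclusion rests on IDH-DS falling under Section 10.1, which the protocol's classification supports and no exemption contradicts.

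IDH-DS is likely to occur in the trial (probability 0.91 to 0.99 of at least one case among 32, if the quoted rates carry over). How many patients would be in direct conflict is unknown.

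A reader might infer that inconsistent handling could tip the decision rule of 3 responses in 20 in the accelerated/blast-phase cohort. The documents do not show this. Removal arises only at Grade 4, whose frequency is not given. The patient would also have to be one who would have responded by cycle 6 but had not yet done so, and the count would have to sit between 2 and 3. The point rests on patient safety and consistent conduct, not on a demonstrated effect on the primary endpoint.

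**What to change.** The sponsor's clinical team should reconcile the passages:

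- State in Section 10.1 whether the general Grade 3/4 rule or Section 10.5 governs IDH-DS.
- Align Section 10.1, Section 10.5 and Appendix D on the hold trigger (including the 48-hour condition), the restart-dose rule with its recovery condition, and the handling of Grade 4 cases.
- Say how the severe category in Appendix D relates to CTCAE grades.
- Check the result against Section 27, which also stops treatment for toxicity needing dose modification or suspension without recovery to baseline in a patient with less than a CRi.

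Which rule is right is a clinical decision, and none is proposed here. The cost is a wording amendment with the usual IRB approval and notice to sites. It needs no new data, procedures or change in sample size.

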-4	5 QD	Stop treatment		
-5	Stop treatment			

* For patients with accelerated and blast phase MF, treatment will continue at the same dose regardless of platelet count.

Table 2b. Ruxolitinib Dose Adjustment for patients with chronic phase MF for thrombocytopenia or nonhematological AEs

Dos	e level	DOSE ADJUSTMENT FOR THROMBOCYTOPENIA		
		Plt>100 X10 ⁹ /L	Plt 50-100 X10 ⁹ /L	Plt 20-50 X10 ⁹ /L
	+1	20 BID	15 BID	N/A
DOSE ADJUSTMENT FOR NON- HEMATOLOGICAL AES	15 BID	10 BID	5 BID*	
	-1	10 BID	5 BID	5 QD
	-2	5 BID	5 QD	Stop treatment
	-3	5 QD	Stop treatment	
	-4	Stop treatment		

MPN-RC

A Phase II Open-label Study of Combined Ruxolitinib and Enasidenib Sinai in Patients with Accelerated/Blast-phase Myeloproliferative Neoplasm or Chronic-

phase Myelofibrosis with an IDH2 Mutation

(Myeloproliferative Neoplasms Research Consortium [MPN-RC] 119)

 Table 3a. Enasidenib Dose Adjustment for thrombocytopenia

MF chronic phase Cycle 1	MF chronic phase Cycle 2 and above	MF chronic phase Cycle 2 and above	MF chronic phase Cycle 2 and above	MF accelerated phase and blast phase
Platelet >75X10 ⁹ /L	Platelet > 50X10 ⁹ /L	Platelet 35-50X10 ⁹ /L	Platelet<35X10 ⁹ /L	Any platelet count
50mg	100mg	50mg	Hold	100mg

Table 3b. Enasidenib Dose Adjustment for non-hematological AE

Dose Level	Enasidenib
-1	50 mg QD
0	100 mg QD

MPN-RC

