10.2 DOSE MODIFICATIONS FOR HEMATOLOGICAL AE'S

For subjects receiving ruxolitinib and enasidenib, ruxolitinib dosages will be adjusted as detailed in **Table 2a** and **Table 2b**.

For chronic phase MF, if platelets are reduced to $< 20X10^{9}/L$ ruxolitinib should be stopped

Ruxolitinib can be rechallenged at 5mg BID when platelets recover to $>20X10^{9}/L$, and enasidenib could be added the subsequent cycle as long as platelets recover to $>50X10^{9}/L$.

Interrupt treatment for absolute neutrophil count (ANC) less than 0.5 X 10^9 /L. After recovery of ANC above 0.75 X 10^9 /L, dosing may be restarted; restart dosing at 5 mg per day lower than the dose prior to the treatment interruption.

For patients with accelerated and blast phase MF, treatment will continue at the same dose regardless of platelet count or ANC.

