10.4 CONCOMITANT MEDICATIONS/TREATMENTS

All supportive measures consistent with optimal subject care will be given throughout the study. Concomitant medications will be captured in the Case Report Form (CRF) beginning at Screening. Packed red blood cell or platelet transfusions are allowed when necessary. Growth factor use (including erythropoietin) is not allowed with the exception of the use of filgrastim (G-CSF) or pegfilgrastim, which is permitted ONLY when used to treat febrile neutropenia or in patients who have prolonged (one week or more) Grade 3-4 neutropenia, after approval from the Study Chair.

Concurrent use of strong inducers of CYP3A4 (Rifampin, St. John's Wort, carbamazepine, phenytoin) and/or the following strong inhibitors of CYP3A4 (protease inhibitor containing HIV antiretrovirals, cobicistat, clarithromycin, itraconazole, ketoconazole, nefadozone, and telithromycin) are prohibited. Also prohibited are CYP2C9 substrate medications that have a narrow therapeutic range: phenytoin and warfarin.

The following medications that are known to prolong QT interval are prohibited: amiodarone, arsenic trioxide, astemizole, azithromycin, bepridil, chloroquine, chlorpromazine, cisapride, citalopram, clarithromycin, disopyramide, dofetilide, domperidone, droperidol, erythromycin, escitalopram, flecainide, halofantrine, haloperidol, ibutilide, levomethadyl, mesoridazine, methadone, moxifloxacin, pentamidine, pimozide, probucol, procainamide, quinidine, sevoflurane, sotalol, sparfloxacin, terfenadine, thioridazine, or vandetanib.

Concomitant use of other cytotoxic chemotherapeutic agents (e.g. anagrelide) or other experimental drug or therapy while the subject is on study is prohibited, except for hydroxyurea.

Patients will be permitted to receive hydroxyurea while on study for a total of 3 cycles of combined therapy to control leukocytosis and thrombocytosis at the discretion of the treating physician. Patients who enter study on hydroxyurea will be permitted to remain on hydroxyurea for a total of 3 cycles of combined therapy. Patients who continue to require hydroxyurea after 3 cycles will be removed from study.

Steroids are allowed for the treatment of IDH-Inhibitor Differentiation Syndrome (IDH-DS), if warranted, as standard of care. The use of chronic low-dose steroids to treat an underlying medical condition that is not a malignancy is permitted during the course of study treatment

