16.8 ABNORMAL LABORATORY VALUES

An abnormal laboratory value is considered to be an AE if the abnormality:

- results in discontinuation from the study;
- requires treatment, modification/ interruption of IP dose, or any other therapeutic intervention; or
- is judged to be of significant clinical importance, e.g., one that indicates a new disease process and/or organ toxicity, or is an exacerbation or worsening of an existing condition.

Regardless of severity grade, only laboratory abnormalities that fulfill a seriousness criterion need to be documented as a serious adverse event.

If a laboratory abnormality is one component of a diagnosis or syndrome, then only the diagnosis or syndrome should be recorded on the AE page/screen of the CRF. If the abnormality was not a part of a diagnosis or syndrome, then the laboratory abnormality should be recorded as the AE. If possible, the laboratory abnormality should be recorded as a medical term and not simply as an abnormal laboratory result (e.g., record thrombocytopenia rather than decreased platelet).

A Phase II Open-label Study of Combined Ruxolitinib and Enasidenib Sinai in Patients with Accelerated/Blast-phase Myeloproliferative Neoplasm or Chronic-

phase Myelofibrosis with an IDH2 Mutation

(Myeloproliferative Neoplasms Research Consortium [MPN-RC] 119)

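### Sections 10.1 and 16.8 can classify an uncomplicated cytopenia that forces a dose hold differently, and nothing says which rule decides the hematological adverse-event rate

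*Combined protocol and SAP*

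**What the plan says.** Section 10.1 states: "Myelosuppression and cytopenias are expected outcomes of MF disease processes and MF treatments and per se will not constitute adverse events except as follows". Two exceptions follow: Grade 4 neutropenia with fever not clinically resolved within 14 days, and Grade 4 thrombocytopenia with clinically significant bleeding. Dose holds, transfusions and anemia are not on that list.

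Section 16.8 is the recording rule for laboratory values. One of its three conditions for an adverse event is that the abnormality "requires treatment, modification/ interruption of IP dose, or any other therapeutic intervention". Its example of preferred terminology is to "record thrombocytopenia rather than decreased platelet".

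Chronic-phase dosing reacts to counts alone:

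- The table headed "Table 3a. Enasidenib Dose Adjustment for thrombocytopenia" lowers enasidenib at platelets of 35-50 × 10⁹/L and holds it below 35, from Cycle 2 on.
- Table 2b sets ruxolitinib by platelet band, and Section 10.2 stops it below 20 × 10⁹/L.
- Section 10.2 also says: "Interrupt treatment for absolute neutrophil count (ANC) less than 0.5" × 10⁹/L.

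For the other cohort, Section 10.2 says: "For patients with accelerated and blast phase MF, treatment will continue at the same dose regardless of platelet count or ANC". Section 10.4 covers supportive care: "Packed red blood cell or platelet transfusions are allowed when necessary". It permits G-CSF for febrile neutropenia or "in patients who have prolonged (one week or more) Grade 3-4 neutropenia", with Study Chair approval.

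Section 13.3 makes the proportion of patients with treatment-emergent hematological adverse events a safety endpoint. Section 22.2 tabulates maximum grade per event type, overall and by cohort. Section 22 plans no summary built directly from blood counts.

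**The concern.** The safety endpoint counts recorded adverse events, so it inherits whatever rule decides what is recorded. If sites follow Section 10.1 literally, a cytopenia that stopped treatment without fever or bleeding, or an anemia that needed transfusion, never enters the hematological rate. If they follow Section 16.8, it does. The study summary lists 11 centers, and two of them could record the same event differently while each follows the protocol. The protocol describes this as the first use of the combination in this population, so its hematological toxicity is a main thing a reader will look for. Section 22 offers no second table in which the discrepancy would show.

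**Working it through.** The plan states no adverse-event rate that depends on this definition, so there is no figure to reproduce. The check is a comparison of rules, followed by simple arithmetic for size.

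**Step 1. Classify the same events under each rule.**

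| Event | Section 10.1, plain reading | Section 16.8 |
|---|---|---|
| Chronic phase, Cycle 2 or later, platelets 30 × 10⁹/L, no bleeding; Table 3a says hold | Not an adverse event | Adverse event (dose interrupted) |
| Chronic phase, ANC below 0.5 × 10⁹/L, no fever; Section 10.2 interrupts treatment | Not an adverse event | Adverse event (dose interrupted) |
| Either cohort, anemia requiring transfusion | Not an adverse event (anemia not listed) | Adverse event (treatment required) |
| AP/BP, low platelets, no dose change, no treatment, not judged clinically important | Not an adverse event | Not an adverse event |

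The first three rows conflict; the fourth does not. The conflict is therefore clearest in the chronic-phase cohort. In AP/BP it arises mainly when a cytopenia is treated or judged clinically important.

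**Step 2. Look for a tie-breaker.** Section 10.2, which contains the count-driven holds, is headed as dose modification for hematological adverse events. Section 10.7 gives significant thrombocytopenia as an example of an adverse event causing an abrupt ruxolitinib hold. Section 16.1 includes laboratory values in the adverse-event definition regardless of cause. All three lean towards Section 16.8, but none says it overrides Section 10.1.

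**Step 3. Weight of one reclassified patient.** Suppose the patient has no other hematological adverse event. The change in the cohort rate is 1/n, with n from Section 21.

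- Chronic phase: 1/10 = 10.0 points (maximum enrolled); 1/9 = 11.1 points (evaluable).
- AP/BP: 1/22 = 4.5 points; 1/20 = 5.0 points.
- Both cohorts, evaluable: 1/29 = 3.4 points.

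For illustration, take three such chronic-phase patients and no other hematological events. The result is 0/9 (exact 95% interval 0 to 33.6%) under Section 10.1, against 3/9 = 33.3% (7.5 to 70.1%) under Section 16.8.

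**Step 4. How often.** The documents give no frequency for such events on the combination. As an assumption only, let q be the per-patient probability, independent across patients. The chance that at least one of nine is affected is 1 − (1 − q)⁹: 37% at q = 5%, 57% at 9%, 87% at 20% and 96% at 30%. This shows sensitivity to q; it is not an estimate.

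**Step 5. The six-patient safety check.** Section 3 limits it to the first 28 days, and Sections 10.1 and 20 require a treatment-related event of Grade 3 or higher. The Table 3a hold applies from Cycle 2, so it falls outside the window. A Cycle 1 ANC interruption, a Cycle 1 platelet-driven ruxolitinib change or a treated Cycle 1 cytopenia could count, if it meets the grade and causality conditions.

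**Step 6. Data available for a remedy.** Table 4 schedules post-baseline blood counts through Cycle 7 Day 1 as follows: Cycle 1 days 8, 15 and 22 (3), Cycle 2 days 1, 8, 15 and 22 (4), Cycles 3-6 day 1 (4) and Cycle 7 day 1 (1). The total is 3 + 4 + 4 + 1 = 12.

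**The case against.** The best defence is that Section 10.1 is a dosing section. Its list can be read as saying when a hematological event makes interruption compulsory, not what goes on the adverse-event form. The same paragraph later allows dose decreases for chronic Grade 3 hematologic toxicity, so its own use of the term goes beyond the two Grade 4 events. *Per se* may mean that only a cytopenia without consequences is excluded. On that view Sections 10.2, 10.7 and 16.8 all agree and there is no conflict.

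This reading is available, and it stops one from calling the two rules irreconcilable. It does not settle the matter. The sentence in Section 10.1 speaks of what constitutes an adverse event, nothing limits it to dosing, and the exceptions name the consequences that count without naming a hold.

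A second defence is that nothing is lost. Section 15 has laboratory abnormalities graded by CTCAE alongside adverse events, counts and transfusion history are scheduled, and drug dosage is on a form. That stands, and it makes the remedy cheap. It does not put a count-based table into Section 22.

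A third is that 10 to 11 points is simply one patient in a small cohort. That is also true: it measures the weight of a misclassification, not its frequency.

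**Conclusion.** The concern holds as an unresolved ambiguity in how a stated safety endpoint is recorded, and it should be fixed. Its size is 10.0 to 11.1 points per affected chronic-phase patient and 4.5 to 5.0 points per affected AP/BP patient, provided the patient has no other hematological adverse event. The number affected cannot be computed from the documents.

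Three stronger conclusions might be inferred, and the documents do not support them:

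- That the sections flatly contradict each other. *Per se*, the heading of Section 10.2 and Section 10.7 leave room for a consistent reading.
- That the enasidenib platelet hold could swing the six-patient check. It starts in Cycle 2, after the 28-day window. In addition, failing the check leads to suspension and review, not automatic closure.
- That the cohorts are unfairly compared. Their dosing rules differ by design, and Section 22.2 plans summaries by cohort, not a comparison.

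The primary endpoint is a response rate and is unaffected.

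**What to change.** 1. In Section 22.2, add worst post-baseline CTCAE v5.0 grade, and shift from baseline, for hemoglobin, platelets and ANC from the scheduled blood counts. Present these by cohort, whether or not an adverse event was reported. Version 5.0 is the version named in the safety objective (Section 7.2). Section 16.2 names only non-hematologic events for CTCAE grading, so align it with Section 15.

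2. Reconcile Sections 10.1 and 16.8, read with 10.2, 10.7, 15, 16.1 and 16.2, into one statement of when a cytopenia is recorded as an adverse event. The sponsor chooses the rule. State that the same rule applies to the six-patient safety check.

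The cost is a few sentences of protocol text and a little more analysis of data already collected. No visits, samples or patients are added, and no dose or treatment rule needs to change for this purpose. The first item is useful whichever recording rule is chosen, because it does not depend on adverse-event reporting.
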